9.7.3 Secondary and Explorative Analyses

The following main categories of inferential analyses will be performed for the secondary endpoints:

- Bayesian estimation of the Sigmoidal dose-response curve will follow the analysis described in Section 9.7.2.3. Prior distributions for primary analysis are specified in Appendix 2, while prior distributions for secondary analyses will be specified in the SAP. The dose-response model for the 50% responder rates will also be further detailed in the SAP.
- Continuous treatment effects at a certain visit will be analysed using SAS PROC MIXED assuming a repeated measures ANCOVA. (A non-parametric dose-response curve is assumed.) The changes from baseline per visit will be regressed upon the baseline observation as covariate and treatment, visit and treatment-by-visit interaction as factors. An unstructured covariance structure will be used for the random subject effect. Least square mean estimates of the changes from baseline and the treatment contrasts (with associated 95% confidence intervals) versus placebo will be tabulated and the changes from baseline will be graphically illustrated. Should only one post-baseline visit be obtained for an endpoint, an ANCOVA will be performed without the visit and treatment-by-visit interaction terms.
- Correlation between endpoints will be reported using Pearson correlation coefficients and partial correlation where applicable.
- Binary endpoints such as “responder status” at a certain visit will be analysed using SAS PROC GENMOD with the logit as link function for the responder probability. An unstructured covariance matrix will be assumed for the repeated responder status which will be adjusted for baseline value as covariate and treatment, visit and treatment-by-visit interaction as factors. (Associated with e.g., responder analysis in terms of reduction in number of voids, cumulative distribution function plots of percentage change from baseline by treatment may be produced.)

Table 9-4 presents the planned analyses.

Illustration of the therapeutic window is described separately in Section 9.7.3.1 and safety related endpoints are further described in Section 9.10.

Explorative gender analyses are planned for all endpoints. For these the following are noted:

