## 10 Efficacy

### 10.1 General Considerations

For endpoints obtained from the Voiding Diary prior to a visit, the average of the endpoint across the 3 days will be interpreted as the cross-sectional observation of the endpoint in question at the specific visit, with the exception of the two endpoints, “Percentage of nights during the treatment period with at most one nocturnal void” and “Percentage of nights during the treatment period with complete response, i.e., with no nocturnal voids”.

If the baseline number of nocturnal voids is missing for a reason that can be considered to be missing completely at random (e.g., missing due to technical problems of the eDiary), the subject will not be included in any analyses that involve baseline measurements of nocturnal voids or other variables derived using baseline measurements of nocturnal voids.

The Bayesian dose-response analyses are conducted on aggregated averages, that is, outcomes averaged across preceding post-randomization visits. The posterior mean, median, and 95% credibility interval (2.5 and 97.5 percentiles of the posterior distribution) of quantities of interest as well as posterior probabilities of interest will be reported.

Frequentist inferences will rely on the appropriate choice of model and report p-values corresponding to the statistical test of the hypothesis of “no difference / no association” against the alternative of “any difference / any (linear) association”. The level of significance is set at 5% (two-sided).

Treatment comparison refers to the pair-wise comparison between each of the different doses of active treatment with FE 201836 and placebo. There are no planned adjustments for multiplicity when pair-wise testing the active treatment with different doses of FE 201836 versus placebo. Desmopressin is included as a benchmark treatment only. None of the primary, secondary or explorative analyses will include data from subjects treated with desmopressin. Explorative benchmarking analyses are further described in Section 10.5.

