Lowest observed change from baseline-RT in Serum Sodium				Alternative safety indicator for therapeutic window	
Incidence and severity of Adverse Events	Section 11.3.1				
Adverse Event of Special Interest: Hyponatraemia Episodes	Section 11.2.1				
Clinically significant changes in laboratory values and vital signs	Sections 11.3.2 and 11.3.3				

a Endpoint assessed at Weeks 1, 4, 8 and 12.

b Endpoints are derived using all diary data collected during the treatment period.

c Endpoint assessed at Weeks 1 and 12.

d Correlation between changes in FUSP and total sleep time at Weeks 1, 4, 8 and 12.

e This questionnaire is retrospective and raw scores will be used in the analysis (not changes from baseline) and the ANCOVA model will not be adjusted for baseline value.

f Endpoint assessed at Weeks 4, 8 and 12.

g Correlation with NPI at Visit 2.

h Endpoint assessed at Week 12.

Illustration of the therapeutic window is described separately in Section 10.4 and safety related endpoints are further described in Section 11.

Explorative analyses by sex are planned for all endpoints, including correlation analyses. For these the following are noted:

- Estimates of the sex-specific dose-response for the aggregated averages after 12 weeks of treatment will follow the Bayesian analysis described in Sections 10.2.1 and 10.3.3 by conducting a separate analysis for each sex. Possible differences between the sex-specific models will be investigated.
- The regression models will be supplemented with an analysis considering sex as well as all interactions between sex and the effects specified in the all-subjects analysis, including any interaction terms specified in the all-subject analysis. Possible differences between the treatment effects for men and women will be evaluated by the treatment-by-visit-by-sex (treatment-by-sex for single-visit outcomes) interaction term with the effect of treatment-by-visit (treatment for single-visit outcomes) included in the model.

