#### **10.3.4 Treatment effects on cross-sectional change from baseline for quantitative variables and PGI-I**

Treatment effects on cross-sectional change from baseline for quantitative variables will be analysed using SAS PROC MIXED assuming a MMRM (a non-parametric dose-response curve is assumed). The systematic effects will comprise visit number and treatment-by-visit as categorical variables, and the baseline-RT value as a linear covariate interacting with visit number. An unstructured covariance matrix will be used if technically possible, alternatively a Toeplitz, a compound-symmetry, or if necessary, an independent covariance matrix will be used. The treatment contrasts (with associated 95% confidence intervals without multiplicity adjustment) versus placebo will be tabulated and graphically illustrated. The analyses will be applied to the observed data on the ITT-RT analysis set.

The same approach will be applied to the aggregated average change from baseline in number of nocturnal voids.

For PGI-I there is no baseline so the systematic effects will comprise only visit number and treatment-by-visit as categorical variables.

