#### 10.4 The therapeutic Window

The estimated sigmoidal dose-response curve with 95% credibility limits compared to placebo (left-sided y-axis) will be illustrated together with the incidence per 100 person-weeks with 95% confidence limits of observation of serum sodium  $<130$  mmol/L and  $\leq 125$  mmol/L, respectively, at or before 12 weeks (both on the right-sided y-axis). The estimated treatment effects with 95% confidence limits compared to placebo for the groups treated with FE 201836 based on the MMRM model described in Section 10.3.4 will also be presented in the graph. The horizontal x-axis will represent the dose range of FE 201836. The therapeutic window is defined as the dose range where FE 201836 is deemed efficacious while the incidence of hyponatraemia is acceptable. Two illustrations will be made with different estimated dose-response curves for the efficacy of FE 201836: one using the results from the primary analysis and one using Sensitivity Analysis 6 based on the actual treatment received.

The sex-specific therapeutic windows will be illustrated similarly.

The therapeutic window of nocturnal volume will be presented similarly.

In addition, similar illustrations of the therapeutic window will be produced using the estimated treatment contrast compared to placebo for the change from baseline-ENR to lowest post-baseline measurement of serum sodium as the safety indicator. To make the results for the efficacy indicator

and the safety indicator comparable in each of these figures, the same treatment definition and the same analysis set will be used for both indicators in each figure.

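### SAP 10.3.4 adds an MMRM fallback ending in an independent covariance matrix, absent from the protocol; if used, it would raise the exploratory sex-interaction test from 5% to about 10–15%

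*SAP*

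**What the plan says.** Protocol 9.7.3 defines the target and the covariance: "Continuous treatment effects at a certain visit will be analysed using SAS PROC MIXED assuming a repeated measures ANCOVA", and "An unstructured covariance structure will be used for the random subject effect". It offers no alternative structure.

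SAP 10.3.4 makes the structure conditional: "An unstructured covariance matrix will be used if technically possible", and otherwise "alternatively a Toeplitz, a compound-symmetry, or if necessary, an independent covariance matrix will be used". It does not say what counts as technically impossible. It names no version with visit-specific variances, no empirical standard errors and no degrees-of-freedom method. The mean model is: "The systematic effects will comprise visit number and treatment-by-visit as categorical variables, and the baseline-RT value as a linear covariate interacting with visit number". The same approach is applied to the aggregated average change in voids.

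Three other places depend on this model or bear on it:

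- **Sex analyses.** SAP 10.3.1 (after Table 5) says: "Possible differences between the treatment effects for men and women will be evaluated by the treatment-by-visit-by-sex" interaction term. These analyses are labelled explorative.
- **Therapeutic window.** SAP 10.4 puts into the figures: "The estimated treatment effects with 95% confidence limits compared to placebo for the groups treated with FE 201836 based on the MMRM model" of 10.3.4. SAP 13 bases risk-benefit on those figures.
- **Sensitivity analysis 7.** SAP 10.2.2 keeps an unstructured matrix for voids, with no fallback.

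SAP 14 itemises other model changes, such as the baseline-by-visit term and the added sex interactions, but not this fallback. Its closing line calls whatever remains a clarification of presentation.

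**The concern.** A subject contributes up to four post-randomisation visits, and Appendix 2 assumes that these are strongly correlated. An independent matrix contradicts that assumption. With model-based standard errors, nothing protects the inference from the wrong structure. A change of covariance model alters standard errors, joint tests and the handling of drop-out, so it is more than a matter of presentation.

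The similar chain in SAP 10.3.5 is a different case: it concerns a GEE working correlation, where standard errors are normally robust to that choice.

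At stake are the visit-specific secondary results, the limits drawn in the therapeutic-window figures, and the test of whether men and women respond differently. The question is which of these an independent matrix would damage, and by how much.

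**Working it through.** **Inputs from the documents.** The nominal level is 5% two-sided (SAP 10.1). Appendix 2 section 4.1.2 gives response fractions f = 0.8142, 0.9328, 0.9874, 1, variance fractions φ = 0.8481, 0.8329, 0.8900, 1, and a between-subject share ω = 0.90. These describe running averages, not visit-specific changes. Drop-out is 15%. The documents state no simulated error rate for the MMRM.

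**1. How likely is the fallback?** Desmopressin is left out of these analyses. Stage 1 has 125 − 25 = 100 relevant subjects. Stage 2 has 175 × 9/10 = 157.5. The total is about 258. With four visits an unstructured matrix has 10 parameters, Toeplitz 4, compound symmetry 2 and independence 1. The last step is reached only after the 10-, 4- and 2-parameter models all fail.

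**2. Implied correlation.** Appendix 2 gives Corr = f_t f_t′ ω / √(φ_t φ_t′). For Weeks 1 and 12: 0.8142 × 1 × 0.90 / √0.8481 = 0.80. For Weeks 4 and 8: 0.9328 × 0.9874 × 0.90 / √(0.8329 × 0.8900) = 0.96. Independence is therefore far from the sponsor's own assumption.

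**3. Single-visit contrasts.** The model gives every visit its own treatment effects and baseline slope. Ignoring within-subject correlation then does not shrink a single-visit standard error; only pooling unequal variances matters. In large samples with complete data:

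rate at visit t = 2 × (1 − Φ(1.96 × √(pooled variance / variance at t)))

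- Equal variances: the ratio is 1, so the rate is 5.0% at any correlation (simulated 4.9–5.2%).
- Appendix 2 running averages: the pooled variance is (0.8481 + 0.8329 + 0.8900 + 1)/4 = 0.893. The rates at Weeks 1, 4, 8 and 12 are 4.4%, 4.2%, 5.0% and 6.4% (simulated 4.5%, 4.2%, 5.1%, 6.4%). At Week 12 the interval is √0.893 = 0.945 of its proper width.

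The simulation had 3,000 trials, 15% drop-out, a baseline-by-visit covariate and assumed arm sizes of 85/15/15/20/25/30/68. Analysing each visit with its own variance held 4.8–5.2%, which reproduces the nominal level.

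**4. The joint sex test.** For a four-visit endpoint it has 6 doses × 4 visits = 24 degrees of freedom. Under an assumed independent matrix, the statistic behaves as Σ λ_j χ²(6), where λ_j are the eigenvalues of the true covariance divided by the pooled variance. Its mean stays at 24, but its variance is 12 Σ λ_j², against the reference 12 × 4 = 48. With equal variances and correlation 0.5, the eigenvalues are 2.5, 0.5, 0.5 and 0.5, so Σ λ_j² = 7 and the variance is 84. The upper tail is too heavy:

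| True covariance | Null rejection rate |
|---|---|
| Equal variance, correlation 0 | 5.0% |
| Equal variance, correlation 0.3 | 7.1% |
| Equal variance, correlation 0.5 | 9.8% |
| Equal variance, correlation 0.7 | 12.6% |
| Equal variance, correlation 0.9 | 15.5% |
| Appendix 2 running averages | 15.1% |

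A simulation with 4,000 trials per setting and assumed arm sizes (85/15/15/15/20/30/78, half women, 15% drop-out) gave 9.7% to 13.7% for correlations of 0.5 to 0.8, and 15.9% for the running averages.

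**5. The earlier fallback steps.** Under compound symmetry the same 24-df test rejected 6.6% (running averages) and 4.4% (equal variance, correlation 0.65) in 3,000 trials with complete data and no baseline covariate. The marked inflation belongs to the independent step.

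**6. Drop-out.** Under independence each visit is estimated from the subjects seen at that visit. A drop-out's earlier visits no longer inform Week 12, so the missing-at-random use of those data is lost.

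**The case against.** The strongest case against has four parts.

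- **The rule is remote.** Three structures must fail first, with about 258 subjects. This stands and keeps the point minor.
- **Only an explorative test is clearly affected.** Proof-of-concept is Bayesian, voids have an unstructured MMRM in sensitivity analysis 7, and NUV, FUSP and the NI Diary scores have their own Bayesian analyses in SAP 10.3.3. This stands too. The 24-df figure also does not apply to every endpoint: ISI has three post-randomisation visits, and NUV has two.
- **A convergence fallback is ordinary SAP detail,** and the protocol delegates detail to the SAP. This stands in part, but a different covariance model is not a clarification of presentation, and SAP 14 lists comparable changes.
- **Empirical (sandwich) standard errors are not a cure.** This stands. With 15 to 20 subjects in a dose group, a dose-by-sex cell holds about 7 to 10, and SAP 14 itself expects 20 or fewer in several groups. In 2,000 null trials with assumed arm sizes, the sandwich version of the joint test rejected about 37%, worse than the 10.6–14.5% under the independent matrix. With about 29 per dose group it was still 20%.

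A reader might infer that error rates double or triple throughout the MMRM. They do not: step 3 shows single-visit contrasts near 5%.

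A reader might also back-solve visit-specific variances from Appendix 2 and find about 13% at Week 12. The documents do not support that figure. They give no visit-specific variances, and Appendix 2 simulates running averages with independent errors. Recovering the last visit as 4y₄ − 3y₃ multiplies the Week 12 error variance of 0.10 by 16, so 1.60 of the resulting 2.68 (in units of σ²) is amplified simulation noise.

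**Conclusion.** The concern holds in a narrow form. SAP 10.3.4 prespecifies a last resort that the protocol lacks, that SAP 14 does not disclose, and that would give an invalid joint sex-interaction test if used: about 10–15% instead of 5% for four-visit endpoints. That range assumes correlations of about 0.5 to 0.9 or Appendix 2's covariance; the supporting simulations also assume the split of subjects across doses. Single-visit contrasts would stay at about 5% with equal variances, or between 4.2% and 6.4% with the running-average fractions. The drop-out consequence is real but has not been quantified. The fallback is unlikely to be triggered and the primary analysis does not depend on it, so this is a desirable correction and not a threat to the trial's conclusions.

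**What to change.** In SAP 10.3.4:

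1. Define failure of the unstructured model, for example non-convergence or an estimated matrix that is not positive definite.
2. Delete the independent covariance option.
3. Replace the chain with heterogeneous Toeplitz, then heterogeneous compound symmetry, both with model-based standard errors.
4. If neither converges, report a separate ANCOVA per visit and test the sex interaction at one time point, fixed in advance as Week 12 or the aggregated average.
5. Do not use empirical standard errors for the multi-degree-of-freedom sex test.

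List the fallback in SAP 14 as a change from Protocol 9.7.3.

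The cost is a few lines of SAP text and a covariance option in the code, with no new data. The last-resort ANCOVA corrects the standard errors and avoids the invalid joint test, but it does not borrow across visits. The loss of earlier-visit information for drop-outs would remain at that step and should be stated if it is used.

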7.1.1.3.1 Patient Global Impression of Severity and Patient Global Impression of Disease Improvement

Patient Global Impression of Disease scales are commonly used measures of symptom severity, treatment response and the efficacy of treatments (Yalcin, 2003). The PGI-I and PGI-S will be included in the trial to indicate change or stability in global health status for anchor-based analyses to identify thresholds for clinically important changes in, e.g., NI Diary scores and number of nocturnal voids, as described in a separate Psychometric Analysis Plan (PAP). Moreover, both scales will be analysed for treatment effect, as described in Section 9.7.3. To better reflect the current condition, the revised and patient-tested versions of PGI-I and PGI-S will refer to 'night-time voiding', as compared to 'LUTS' (Viktrup, 2012).

The PGI-S is a prospective measure that measures a patient's current severity reported as "None," "Mild," "Moderate," or "Severe" (coded as 1-4). Scores on this measure will provide a patient-rated summary of the severity of the patient's nocturia symptoms.

The PGI-I is a retrospective measure. It will provide a patient-rated summary of change in nocturia since the start of trial treatment, reported as "Very much better," "Much better," "A little better," "No change," "A little worse," "Much worse," or "Very much worse," (coded as 1-7).

PGI-S followed by PGI-I will be completed by the subjects at home in the evening immediately after completing the NI Diary, as outlined in Figure 3-2 and Figure 3-3.

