### 3.1.2 Sample Size

A maximum of 300 subjects (males and females) will be randomized into the trial. The sample size was based on computer simulations under five sigmoidal dose-response profiles without baseline adjustment. The operating characteristics and associated power were estimated for the different dose-response scenarios by computer simulations using the Fixed and Adaptive Clinical Trial Simulator (FACTS) version 5.6.

The average number of subjects and probabilities for futility and success are presented in Table 2.

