#### 6.1.6 e-Diary Assessments at Baseline

The baseline registrations in the e-Diary include a Voiding Diary, a Nocturia Impact Diary, PGI-S, ISI, and Bother. Based on the baseline registrations in the Voiding Diary, baseline values for several variables are derived: number of nocturnal voids, nocturnal urine volume, NPI, nocturnal diuresis rate, FUSP, and total sleep. The Nocturia Impact Diary is used to derive the baseline values of the two NI Diary endpoints, NI Diary Total Score and the overall QoL impact question.

Baseline-ENR values of the e-Diary variables will be summarized overall for the ITT-ENR analysis set. Baseline-RT values of the e-Diary variables will be summarized overall and by treatment group for the ITT-RT analysis set.

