#### 10.3.6 Treatment effects on single-time-point quantitative variables

Treatment effects on single-time-point quantitative variables will be analysed using SAS PROC MIXED to perform an ANCOVA (a non-parametric dose-response curve is assumed). For the percentages of nights with response, the systematic effects will comprise treatment as a categorical variable and baseline-RT number of nocturnal voids minus 2 as a linear covariate. For change from baseline-RT in copeptin, the systematic effects will comprise treatment as a categorical variable and the baseline-RT level minus 13.1 as a linear covariate. For change from baseline-RT to lowest observed serum sodium, the systematic effects will comprise treatment as a categorical variable and the baseline-RT level minus 135 as a linear covariate. The treatment contrasts (with associated 95% confidence intervals without multiplicity adjustment) versus placebo will be tabulated and graphically illustrated. The analyses will be applied to the observed data on the ITT-RT analysis set. For change from baseline-RT to lowest observed serum sodium, the analyses will be performed both using randomized treatment for the observed data on the ITT-RT analysis set for comparability with the results for the efficacy variables and using actual treatment for the Safety-RT analysis set for comparability with the analyses of episodes of hyponatraemia based on observed serum sodium.

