In addition to the illustrations of the therapeutic window specified in the protocol, illustrations of the therapeutic window will be produced using the estimated treatment contrast compared to placebo for the change from baseline-RT to lowest post-baseline measurement of serum sodium as the safety indicator. The inclusion of desmopressin in the plots illustrating the therapeutic window (“Corresponding efficacy and safety of desmopressin will be illustrated in a side panel for comparison.”) has been deleted to comply with “None of the primary, secondary or explorative analyses will include desmopressin.” (Section 10.1).

In the analyses of time to ‘confirmed’ hyponatraemia episodes, the time to event is defined as the time of confirmation in stead of the time to first measurement below the threshold to avoid conditioning on the future. The protocol states “The associated relative hazards of treatment and gender will be analysed using Cox proportional hazards model adjusting for baseline serum sodium and age (<65,  $\geq$ 65 years). Possible heterogeneity between the genders in the relative treatment hazards will be explored by the inclusion of a treatment-by-gender interaction term”. These analyses will not be performed since the trial is too small to perform Cox regression analyses of the occurrence of hyponatraemia events with 9 treatment groups and 2 covariates.

The adverse events tables presenting incidences of least 5% have been changed to presenting at incidences of at least 10% because it is expected that for several of the FE 201836 treatment groups, 20 subjects or less are allocated to the group.

According to [REDACTED], the interim analyses will deviate from the Appendix 2 in the protocol regarding the derivation of the allocation probabilities by the factor  $1/(n_d + 1)$  before the normalization to sum to 1.

Remaining changes are all considered clarifications of presentations specified in the protocol.

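### The PGI-I model omits baseline severity although PGI-S is recorded at Visit 4; adding it is a cheap precision gain, not the repair of an error

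*SAP*

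**What the plan says.** SAP 10.3.4 fits a mixed model for repeated measures to each quantitative endpoint, with visit, treatment-by-visit and the endpoint's own Visit 4 value by visit. PGI-I is the exception: "For PGI-I there is no baseline so the systematic effects will comprise only visit number and treatment-by-visit as categorical variables". SAP Table 5 footnote e gives the same instruction, that "the ANCOVA model will not be adjusted for baseline value", and protocol Table 9-4 footnote b agrees.

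The reason lies in the instrument. Protocol section 7.1.1.3.1 describes PGI-I as retrospective: "It will provide a patient-rated summary of change in nocturia since the start of trial treatment". It is asked only after randomisation.

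Other severity measures are available at baseline. SAP 6.1.6 states: "The baseline registrations in the e-Diary include a Voiding Diary, a Nocturia Impact Diary, PGI-S, ISI, and Bother". Protocol Table 6-1 and SAP Table 3 both schedule PGI-S at Visit 4.

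On arm size, SAP section 14 expects that "for several of the FE 201836 treatment groups, 20 subjects or less are allocated to the group". The protocol synopsis describes unrestricted randomisation among the FE 201836 doses, and no stratification by baseline severity is described.

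**The concern.** A covariate does not have to be on the outcome's scale. It needs to be measured before randomised treatment and to predict the outcome. Baseline PGI-S meets the first condition and may meet the second: it is completed alongside PGI-I at each later visit, and both refer to night-time voiding.

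The SAP does not treat the lack of a same-scale baseline as decisive elsewhere. In section 10.3.6 the percentage-of-nights endpoints are adjusted with "baseline-RT number of nocturnal voids minus 2 as a linear covariate", and in section 10.3.5 responder status is adjusted for log-transformed baseline voids by visit.

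Each dose-versus-placebo contrast for PGI-I is reported with a 95% confidence interval. If severity predicts PGI-I, an unadjusted contrast for a dose arm of about 20 includes whatever severity difference arose by chance, and its interval is wider than the collected data require.

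**Working it through.** **1. Arm sizes.** Inputs: "A maximum of 300 subjects (males and females) will be randomized into the trial" (SAP 3.1.2); the first 125 subjects at 2:2:1 and the rest at 2:7:1 for placebo, FE 201836 and desmopressin (SAP 3.1.1); desmopressin left out of the analysis (SAP 10.1).
- Placebo: 50 + 0.2 × 175 = 85.
- FE 201836 in stage 2: 0.7 × 175 = 122.5, or 122.5 / 6 = 20.4 per dose on average. With uneven adaptive allocation, several doses at or below 20 is what one would expect, so the SAP's own figure is reproduced.
- Desmopressin: 25 + 0.1 × 175 = 42.5. Analysed: 300 − 42.5 = 257.5, taken as 257 in 7 arms.

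**2. Chance imbalance in baseline severity, 20 against 85.**
- SD = √(1/20 + 1/85) = √0.06176 = 0.249 baseline SD.
- 95% range: ±1.96 × 0.249 = ±0.49 baseline SD.
- Probability of an imbalance above 0.25 SD in either direction: 31%; above 0.5 SD: 4%.

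**3. Effect of adjusting.** R is the within-arm correlation of PGI-I with baseline PGI-S. It is not in the documents, so a range is assumed. For one covariate, N = 257 and g = 7 arms:

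variance ratio, adjusted / unadjusted = (1 − R²) × (1 + 1/(N − g − 2)) = (1 − R²) × (1 + 1/248)

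The SE ratio is its square root. The equivalent sample-size gain is 1/(variance ratio) − 1. The last column is the shift in the unadjusted PGI-I contrast, in PGI-I SD, from an imbalance at the edge of the 95% range: R × 1.96 × 0.249.

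| R | SE ratio | Equivalent gain in N | Shift from a 0.49 SD imbalance |
|---|---|---|---|
| 0 | 1.002 | -0.4% | 0 |
| 0.1 | 0.997 | 0.6% | 0.05 |
| 0.2 | 0.982 | 3.7% | 0.10 |
| 0.3 | 0.956 | 9.4% | 0.15 |
| 0.4 | 0.918 | 18.6% | 0.20 |

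Break-even: R ≈ √(1/248) = 0.06. With 15% fewer subjects, the dropout assumed in protocol section 9.1, it is 0.07.

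**4. Validity of the planned analysis.** A single-visit simulation used 85 placebo subjects, five arms of 20 and one of 70, with 4,000 runs at each of R = 0, 0.1, 0.3 and 0.5. The mean unadjusted contrast stayed between -0.002 and 0.006 SD, so there was no average bias. Type I error was 4.5–6.3% unadjusted and 4.2–5.7% adjusted (with two covariates, one of them predictive). The 6.3% is simulation noise: with normal errors this test is exact, and repeating the unadjusted test three times with 20,000 runs per value of R gave 4.7–5.2%.

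**5. Why not void counts.** SAP 10.1 and section 14 remove subjects with a missing baseline voiding diary from every analysis that uses baseline voids. Those subjects can enter PGI-I as now planned. Adjusting for voids would cancel its own gain once the share lost exceeds 1 − variance ratio: 0.6% at R = 0.1, 3.6% at 0.2, 8.6% at 0.3. The SAP does not say how many subjects are affected.

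**Limit of the calculation.** It covers one visit. The proposed term has four slopes, one per visit, but each visit's contrast is adjusted mainly through its own slope, so the cost per contrast should stay close to the one-parameter figure.

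**The case against.** The strongest reply is that the choice is deliberate, stated alike in protocol and SAP, and harmless. PGI-I is one of many secondary endpoints, plays no part in the success criterion, and has a baseline-adjusted companion in the PGI-S change analysis. Ordinary chance imbalance is already reflected in the confidence interval, and baseline e-Diary values will be tabulated by arm. All of that stands. It makes this a refinement, but gives no reason to prefer the less precise analysis.

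The gain may also be small. PGI-I already rates change, PGI-S has four levels, and entry requires at least two nocturnal voids at Visits 2 and 4, which narrows baseline severity. This stands too, and is why the range starts at R = 0.

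The comparison with sections 10.3.5 and 10.3.6 is imperfect, because those endpoints are derived from void counts and baseline voids is their natural baseline. That is fair. They show only that the SAP adjusts outcomes with no baseline in the same form.

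Finally, PGI-I looks back to the start of trial treatment, and the active run-in precedes Visit 4, so Visit 4 severity may not be the subject's reference point. This could lower R. It does not affect validity, since any value recorded before randomised treatment is admissible.

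**Conclusion.** The point holds as a low-priority improvement in precision. PGI-I is left without a covariate for a reason that excludes only its own baseline, while its companion severity scale is scheduled at Visit 4 and already used in the PGI-S model. The size rests wholly on the assumed R: from a 0.4% loss at R = 0 to an 18.6% gain at R = 0.4, with break-even near 0.06.

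Three stronger readings are not supported:
- A reader might infer that the planned PGI-I result is biased or invalid. Randomisation makes the unadjusted contrast unbiased on average, and its type I error is 5%.
- A reader might infer that adjustment costs nothing. It costs a little precision if R is near zero, needs a missing-value rule, and with void counts could lose subjects.
- A reader might infer that a gain of roughly 4–19% is established. That range is R = 0.2 to 0.4, and the documents contain no estimate of R.

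**What to change.** Before unblinding, make these changes:
- In SAP 10.3.4, add baseline-RT PGI-S to the PGI-I model as a linear covariate interacting with visit.
- Set any missing baseline-RT PGI-S to the mean over all analysed subjects, pooled across arms, so that no subject is lost and the fill does not depend on treatment. The documents report missing baselines only for the voiding diary, but PGI-S is in the same e-Diary, so the rule is needed.
- Amend Table 5 footnote e to match.
- Record the departure from protocol Table 9-4 footnote b in SAP section 14, which already lists comparable added model terms.
- Do not use baseline void count as the covariate.

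The cost is one model term (four slopes), one missing-covariate rule, two text amendments and a deviation entry. Under SAP 10.3.1 the sex-interaction version of the model would carry the term as well. The loss of degrees of freedom is negligible: about 0.2% in the standard error if PGI-S turns out not to predict PGI-I.
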